- d. Lofexidine/Placebo Titration Procedures (Days 8-17). After two consecutive negative drugs screens have been obtained, participants will be randomly assigned to study medication (lofexidine or matching placebo). For the Shoreline site, medication will be dispensed by IDS and delivered to MUSC staff at that site. At the randomization visit, females will provide saliva samples for estradiol and progesterone testing. Trained study personnel will evaluate heart rate, orthostatic blood pressure, and pre-syncope and syncope signs and symptoms prior to the initiation of Lofexidine. Lofexidine will not be dispensed if the participant is found to have

one of the following on physical exam: 1) clinically significant bradycardia as determined by study physician; 2) orthostatic hypotension defined as a systolic blood pressure decrease of at least 20mm Hg or a diastolic blood pressure decrease of at least 10mm Hg within three minutes of standing; 3) participant endorsement of presyncope symptoms such as lightheadedness, muscular weakness, blurred vision, or feeling faint during the evaluation of orthostatic blood pressure; or 4) syncope (fainting) during the evaluation of orthostatic blood pressure. Participants with bradycardia, orthostatic hypotension, pre-syncope or syncope would be terminated from the study and study staff will facilitate appropriate follow-up medical care. To minimize risks of hypotension, lofexidine will be titrated over a 10-day period with 0.36 mg QDfor days 1 and 2; 0.36 mg BID for days 3 and 4; 0.36 mg TID for days 5 and 6; 0.36 mg BID and 0.72 QD days 7 and 8; 0.37 QD and 0.72 BID for days 9 and 10, and 0.72 mg TID on day 11 and throughout the rest of the study (see **Table 2**). This is the dose recommended by the regulatory agencies in England and the titration schedule is consistent with lofexidine titration in 8 published studies (Gish et al., 2010).

Table 2

| Days                                      | AM Dose (mg) | PM Dose (mg) | QHS Dose (mg |
|---|--------------|--------------|--------------|
| Days 1 and 2 (Study days 8 and 9)         |              |              | 0.36         |
| Days 3 and 4
(Study days 10 and
11) | 0.36         |              | 0.36         |
| Days 5 and 6 (Study days 12 and 13)       | 0.36         | 0.36         | 0.36         |
| Days 7 and 8 (Study days 14 and 15)       | 0.36         | 0.36         | 0.72         |

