| Days 9 and 10 (Study days 16 and 17)      | 0.36         | 0.72         | 0.72         |
| Days 11-40
(Study days 18-40)          | 0.72         | 0.72         | 0.72         |

Trained study personnel will evaluate heart rate, orthostatic blood pressure, pre-syncope and syncope signs and symptoms at all study visits during the titration period. If the study participant does not have bradycardia, orthostatic hypotension, or pre-syncope or syncope signs or symptoms as defined above, the dose of Lofexidine will be increased according to the titration schedule (**Table 2**). If bradycardia, orthostatic hypotension, or signs/symptoms of pre-syncope or syncope are identified at any point, the dose of Lofexidine will be lowered to the prior tolerated Lofexidine dose and the participant will remain at that dose for the duration of the study. At the beginning of the study, participants will be given a rescue pack of 36 tablets in case visits are missed. This will cover 3 days at the full dose.

The medical provider will inform the participant, verbally and with a take-home hand-out, of common side effects of lofexidine (dizziness, somnolence, dry mouth) and precautions to minimize risks associated with blood pressure (BP) decreases (hydration, standing up slowly). Participants will attend study visits three times a week during the induction period and throughout the study during which a UDS will be collected. The MUSC Investigational Drug Service will be responsible for randomization, will keep a record of the blind and will be available should unblinding be required. In the event that WorldMeds is unable to supply matching placebo. lofexidine tablets (supplied by US WorldMeds) will be encapsulated along with matching placebo capsules by Pitt Street Pharmacy, a specialty compounding pharmacy. Randomization will be stratified on presence/absence of other substance use as well as the presence/absence of significant childhood trauma (ACE>4).

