e. Medication maintenance and adherence monitoring (Days 18-40). Trained study personnel will evaluate heart rate, orthostatic blood pressure, pre-syncope and syncope signs and symptoms once per week following the Lofexidine titration. If bradycardia, orthostatic hypotension, or signs/symptoms of pre-syncope or syncope are identified at any point, the dose of Lofexidine will be lowered to the prior tolerated Lofexidine dose and the participant will remain at that dose for the duration of the study. Participants will record themselves taking their medications A survey link will be sent to the participant's cell phone via app alert two to three times daily, depending on where they are in the medication schedule. Video capture will occur through the CREMA app. The research coordinator will review the subjects' videos before each study visit. As discussed, we have used this

technology successfully for medication adherence monitoring. To encourage compliance, participants will receive \$10 for each day that they complete their medication adherence videos.

- **f. Intervention phase** (Study Days 18-40). During the 5-week medication phase, study participants will come in three times per week for UDSs. Blood pressure and pulse will be assessed at each visit. If the SBP < 90 mmHg and > 20% below screening value and/or DBP is < 50 mmHg and > 20% below screening value, or the individual is complaining of symptoms of hypotension, the medication dosage will be reduced. If these symptoms do not resolve, the individual will be removed from the study and followed until vital signs normalize. EKG's will be performed at Weeks 4 and 6 to monitor QT intervals. A contingency-management procedure will be implemented to facilitate study visit adherence. The payments will start at \$4 and increase by \$4 for each consecutive visit.

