- g. Virtual monitoring: In order to reduce face-to-face visits when necessary, remote monitoring may be done during the medication phase. At the randomization visit, patients will be given a wrist blood pressure cuff for at home monitoring, and they will be trained in testing orthostatic blood pressure. Patients will come to the clinic once a week for a UDS, to meet with staff/medical personnel and have ave orthostatic testing done, and receive medication refills. Two weekly visits will be conducted via Telehealth. Patients will be observed doing a saliva drug screen and doing orthostatic blood pressure testing. If patients are symptomatic or having difficulty with telehealth procedures, they may be asked to attend the clinic more frequently. Participants who are not comfortable with telehealth procedures may choose to attend clinic visits instead.
- C.2.c.5. Phase Two: Scripted Opioid Imagery and Laboratory Induction Session (Days 39 and 40). At the end of the five-week period of lofexidine or placebo administration, participants will return to complete a scripted opioid imagery taksk and a laboratory stress task (Trier Social Stress TSST). Tasks will Test, counterbalanced. Subjects will remain on study medications for the test days. Subjects who miss their scheduled visits may be re-scheduled for up to one week. a. Session Preparation. Participants will be instructed to arrive at 8:00am on the test days, and to avoid caffeinated beverages since caffeine can introduce variability in heart rate response. If the individual is nicotine-dependent, (s)he will be provided with a nicotine patch throughout their study visit. Upon arrival, the participant will be breathalyzed and

|            | TAB             | BLE 3: LAB TESTING TIMELINE                                |  |  |
|------------|-----------------|--|--|--|
|            | 8:15am          | UDS, Saliva  |  |  |
|            | 8:35 am         | Relaxation   |  |  |
| Test Day 1 | 8:55am          | Baseline 1 Subjective, physiologic, endocrine measurement  |  |  |
| st [       | 9:00am - 9:15am | TSST/Imagery   |  |  |
| Te         | 9:15am          | Subjective, physiologic, endocrine measurement             |  |  |
|            | 9:20am          | Subjective, physiologic, endocrine measurement             |  |  |
|            | 9:45am          | Subjective, physiologic, endocrine measurement             |  |  |

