#### b. Protections Against Risks

All study participants will be closely monitored for psychiatric and medical stability. All sessions will be conducted under the supervision of experienced personnel. If crisis intervention is necessary, senior staff will be available to evaluate the subject and provide an intervention or referral. If hospitalization is indicated, the patient will be hospitalized through the Center for Drug and Alcohol Programs at MUSC or an appropriate referral will be made. All participants will be fully informed that they may withdraw from the study at any time without penalty.

Lofexidine will be titrated over ten days when it is initiated. Participants will be seen by a medical provider on three times a week uring dosage escalation and orthostatic hypotension testing will be done. The medical provider will inform the participant, verbally and with a hand-out to take home, concerning common side effects of lofexidine (dizziness, somnolence, dry mouth) and precautions to minimize risks associated with blood pressure decreases (hydration, standing up slowly). The target dose of lofexidine is 2.16 mg per day, but if hypotension or other troublesome side effects develop, the medical provider may slow the titration for that individual. At the end of the study, medications will be tapered over a five-day period. Participants will be seen every other day during medication taper and blood pressure will be monitored.

To ensure confidentiality, all participant data will be coded by letters and/or numbers, and only the investigators will have access to the master lists of codes. All participant records will be kept in a locked cabinet in an office that will be locked at times when not in use. Participants who screen remotely and have virtual medication monitoring visits will be instructed to find a private location to conduc these visits. The research staff understands the importance of maintaining confidentiality, and this method of maintaining confidentiality has been used for several years by our research group and has been effective. All electronic databases are stored on HIPAA-compliant servers with restricted access. All co-investigators and study personnel have completed (or will complete upon hiring) training in Good Clinical Practices as mandated by NIH and the MUSC IRB.

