## Regulatory Issues.

Potential conflicts of interest will be reported using the upcoming NIH rules for disclosure. Adverse Events (AEs)/Serious Adverse Events (SAEs) occurring during the course of the project will be collected, documented, and reported in accordance with protocol and IRB reporting requirements. All research staff involved with adverse event reporting will receive general and protocol specific AE/SAE training including identification, assessment and evaluation, and documentation and reporting. A research assistant will identify any potential adverse events during the course of the study from participant self-report and administration of the visit assessments and procedures. The research assistant will provide information to a study physician, who will be responsible for AE/SAE assessment and evaluation including a determination of seriousness and study relatedness. Any significant actions taken by the local IRB and protocol changes will be relayed to ORWH/NIDA.

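### Required orthostatic testing drops from every clinic visit to once a week on Study Day 18, the same day lofexidine reaches its 2.16 mg/day maximum

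*Combined protocol and SAP*

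**What the plan says.** All references are to the combined protocol and SAP.

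- **Titration (Section C.2.c.5, item d, headed Days 8-17).** Staff check heart rate, orthostatic pressure and pre-syncope or "syncope signs and symptoms at all study visits during the titration period". A positive finding lowers the dose for the remainder of the study, with or without symptoms.
- **Dose schedule (same item, and Table 2).** The final level is "0.72 mg TID on day 11 and throughout the rest of the study". Table 2 equates medication day 11 with Study Day 18.
- **Maintenance (item e, headed Days 18-40).** The same evaluation is required for "signs and symptoms once per week following the Lofexidine titration". The item does not say which of the three weekly visits carries it.
- **Intervention phase (item f, Days 18-40).** "Blood pressure and pulse will be assessed at each visit". The dose is cut for low absolute readings that are also more than 20% below screening, or for hypotensive symptoms. No standing measurement is specified.
- **Virtual monitoring (item g).** There is one clinic visit a week with orthostatic testing. For the two telehealth contacts, "Patients will be observed doing a saliva drug screen and doing orthostatic blood pressure testing".
- **Protections Against Risks (Section 2.b).** Visits are "three times a week uring dosage escalation and orthostatic hypotension testing will be done". The same section states: "Lofexidine will be titrated over ten days when it is initiated".

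**The concern.** A test schedule meant to catch blood pressure effects of dose increases should still be running at the first visit after the last increase. Here the required frequency falls on the day that increase is made.

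The protocol gives an orthostatic drop real weight. Before dosing it ends participation, and during dosing it lowers the dose permanently even when the participant feels well. A clinic participant whose drop first appears at 2.16 mg/day, without symptoms, could attend one or two visits on that dose before a standing test is due. The issue is participant safety. Nothing here suggests a difference between arms in how outcomes are measured.

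**Working it through.** **Dose by step.** Summing the morning, afternoon and bedtime doses in Table 2:

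| Study days | Sum (mg) | Daily total (mg) | Increase over previous step |
|---|---|---|---|
| 8-9 | 0.36 | 0.36 | - |
| 10-11 | 0.36 + 0.36 | 0.72 | 100% |
| 12-13 | 3 × 0.36 | 1.08 | 50% |
| 14-15 | 0.36 + 0.36 + 0.72 | 1.44 | 33% |
| 16-17 | 0.36 + 0.72 + 0.72 | 1.80 | 25% |
| 18 onward | 3 × 0.72 | 2.16 | 20% |

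The last total reproduces the 2.16 mg target in Protections Against Risks. Medication day 11 is Study Day 11 + 7 = 18, the first day of the once-weekly rule.

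**Visit calendars.** The documents give three visits a week but no weekdays. Assume Monday/Wednesday/Friday visits, with the randomization visit (Day 8) on any weekday.

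| Weekday of Day 8 | Visits to Day 24 | Last required test before Day 18 | First visit after Day 16 | First visit after Day 18 | Last visit in Days 18-24 |
|---|---|---|---|---|---|
| Mon | 8, 10, 12, 15, 17, 19, 22, 24 | 17 | 17 | 19 | 24 |
| Tue | 8, 9, 11, 14, 16, 18, 21, 23 | 16 | 18 | 21 | 23 |
| Wed | 8, 10, 13, 15, 17, 20, 22, 24 | 17 | 17 | 20 | 24 |
| Thu | 8, 9, 12, 14, 16, 19, 21, 23 | 16 | 19 | 19 | 23 |
| Fri | 8, 11, 13, 15, 18, 20, 22 | 15 | 18 | 20 | 22 |

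**Is a standing test guaranteed at the next visit after the step?** It is if that visit falls in Days 8-17.

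- Steps on Days 10, 12 and 14: the next visit is by Day 16 in every calendar, so 5 of 5.
- Step on Day 16: 2 of 5 (Mon, Wed) counting later visits only. Counting a same-day visit adds Tue and Thu, giving 4 of 5.
- Step on Day 18: 0 of 5 on either count.

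**Delay from the Day 18 step to the first required test.**

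- Weekly test at the first visit after Day 18: 1, 3, 2, 1 and 2 days (Mon to Fri starts).
- Weekly test on Day 18 itself, possible only for Tue and Fri starts: 0 days. At most the first enlarged morning dose has then been taken.
- Weekly test at the last visit in Days 18-24: 6, 5, 6, 5 and 4 days. Between Day 19 and that test, 2, 1, 2, 2 and 1 visits pass without a required standing test.

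The Friday start is the weakest case. The last required test is on Day 15 at 1.44 mg/day, two increases follow, and the next required test can be as late as Day 22.

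**Would the every-visit checks find the drop?** Item d defines orthostatic hypotension as a fall of at least 20 mm Hg systolic or 10 mm Hg diastolic within three minutes of standing. Item f acts on readings below 90 systolic or 50 diastolic. As an invented illustration, 120/75 sitting and 98/64 standing is a fall of 22/11, which meets the item d definition. Neither standing value is below the item f limits, so without symptoms item f would not trigger even if the standing reading were the one taken.

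**The case against.** The best counter-argument is that Day 18 belongs to titration. The 0.72 mg three-times-daily level is stated in the titration sentence, Table 2 serves as the titration schedule and includes that row, and Protections Against Risks links testing to escalation, which a rise from 1.80 to 2.16 mg is. Staff could read it that way. But the section headings divide at Day 17/18, and the titration is twice given as ten days, so the text favours the other reading. If every-visit testing was meant to cover Day 18, the protocol should say so.

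Several other points stand and limit the weight of the finding:

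- The final step is the smallest in proportion (20%). It changes only the morning dose, and single doses of 0.72 mg have been taken since Day 14.
- In every assumed calendar a required standing test falls on Days 15-17, shortly before the step.
- Blood pressure, pulse and a symptom rule apply at each visit. Item e acts on a problem found at any time, and under Regulatory Issues staff "identify any potential adverse events during the course of the study from participant self-report and administration of the visit assessments and procedures". Participants are also counselled on hydration and standing slowly.
- The 0 of 5 count follows directly from Day 18 lying outside Days 8-17 and needs no weekday assumption. The Day 16 counts and the delays do depend on the assumed calendar.

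None of these protections specifies a sitting-to-standing comparison at the first clinic visit on the full dose.

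**Conclusion.** The concern holds for clinic-monitored participants. Required standing tests fall from three a week to one on the day of the last increase, so none is guaranteed at the next visit. The first required test comes 0 to 3 days after the step if the weekly test is placed early, and 4 to 6 days after if it is placed late. Those delays assume Monday/Wednesday/Friday visits.

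The exposure is narrow: an asymptomatic postural drop without a qualifying low reading. The documents give no rate for this, so no participant count can be offered. Participants on virtual monitoring are outside the finding, because orthostatic testing is part of all three of their weekly contacts. The change should be made as an inexpensive safety improvement. It does not affect the validity of the treatment comparison.

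**What to change.** In Section C.2.c.5, item e, require the heart rate, orthostatic pressure and pre-syncope/syncope evaluation at every study visit in Days 18-24, and at least once a week from then to Day 40. The Day 18 step then has a required standing test at the next visit in all five assumed calendars. So does the Day 16 step, whose next visit is Day 17, 18 or 19.

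The cost is one sentence of protocol text. Each calendar has three visits in Days 18-24, one of which already carries the weekly test, so at most two tests of a few minutes are added per clinic participant. They fall at visits where blood pressure and pulse are already taken, and no visits are added.

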|            | 10:15am         | Subjective, physiologic, endocrine measurement             |  |  |
|            |                 |  |  |  |
|            | 815am           | UDS, Saliva  |  |  |
|            | 8:35am          | Relaxation   |  |  |
| Day 2      | 8:55am          | Baseline 1: Subjective, physiologic, endocrine measurement |  |  |
|            | 9:00am          | Opioid imagery/TSST  |  |  |
| Test       | 9:05am          | Subjective, physiologic, endocrine measurement             |  |  |
| _          | 9:10am          | Subjective, physiologic, endocrine measurement             |  |  |
|            | 9:35am          | Subjective, physiologic, endocrine measurement             |  |  |
|            | 10:05 am        | Subjective, physiologic, endocrine measurement             |  |  |

will provide a urine sample to be tested for drugs of abuse. For women, a pregnancy test will be done prior to the urine drug screen, and saliva will be collected for estrogen and progesterone measurement.

- **b.Progesterone and Estrogen.** As there is significant individual variability in progesterone and estrogen levels across the menstrual cycle, measurement of progesterone and estrogen at the time of testing in combination with the menstrual cycle history will allow us to approximate the menstrual cycle phase as well as to utilize all participants' data with absolute progesterone and estrogen levels as continuous measures.
- **c. Design timing.** Subjects will first undergo a progressive relaxation task. Baseline assessments of subjective, hormonal (cortisol), and physiologic measures (blood pressure and heart rate) will be collected following relaxation, 5 minutes before the stressor or imagery; TSST takes 15 minutes, and the imagery takes 5 minutes. At the end of the stressor of drug cue, a salivary sample will be collected to assay cortisol and physiological (blood pressure and heart rate) and subjective measures (Mood Rating Scale, Opioid Craving Questionnaire, STAI) will be obtained. Measurements will also be obtained at 5- 30-, and 60-minutes post-task.
- d. Trier Social Stress Task (TSST) is a standardized psychological stress challenge which has been used extensively in research studies. A meta-analysis supports its utility for evoking a HPA axis stress response in a laboratory setting (Dickerson & Kemeny, 2004). It has induced a robust and reliable physiological stress

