Statistics and Data Analysis (complete statistical/data analysis plan in Biostatistics Resource Core): Aim 1: Using a human laboratory paradigm, determine the impact of lofexidine on stress and drug cueinduced craving in women and men with OUDs: The primary study outcome of interest in Aim 1 is the differential craving, stress and anxiety response to a human laboratory paradigms containing both a stressor (TSST) and an opioid specific cue between participants randomized to lofexidine and placebo in addition to buprenorphine/methadone maintenance. Hypothesis 1: Lofexidine will attenuate drug craving and subjective stress response to a stress task in opioid-dependent individuals compared to individuals receiving placebo. Hypothesis 2: Lofexidine will attenuate drug craving and subjective stress response to a drug-related cue in opioid-dependent individuals. Hypothesis 3: The ameliorative effects of lofexidine on stress and cue-reactivity will be more pronounced in females than male subjects. To assess the hypothesis that lofexidine will attenuate drug craving and subjective stress response to the stressor and the opioid-related cue task, multilevel longitudinal GLMMs will be developed using all post-stressor and post-cue data. Initial models will control for study design aspects such as order (stressor or cue first), treatment assignment, and baseline craving and stress (task level). Covariate adjusted models will additionally include baseline characteristics determined to be correlated with study outcomes or those determined to be significant effect modifiers. To examine the differential effects of lofexidine on stress and cue-reactivity across female and male subjects, the models will have additional parameters added to include an indicator of participant gender and the interaction between gender and randomized treatment assignment. Relevant interactions will be assessed in all models. Least square means and associated standard errors will be assessed to compare craving and subjective stress response between treatment assignments at all time points.

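### Table 3 fixes the laboratory sampling times by test day although task order is counterbalanced, so for imagery-first participants its times conflict with the text

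*Combined protocol and SAP*

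**What the plan says.** Section C.2.c.5, Phase Two, places the two laboratory tasks on Days 39 and 40. The sentence on order is garbled ("Tasks will Test, counterbalanced"), but the meaning is clear, because the Aim 1 analysis in section C.2.d adjusts for "order (stressor or cue first").

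Table 3 is consistent with that. The Day 1 row reads "9:00am - 9:15am | TSST/Imagery" and the Day 2 slot, starting at 9:00, reads "Opioid imagery/TSST". Each day has a single list of measurement times:

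- Day 1: 9:15, 9:20, 9:45 and 10:15.
- Day 2: 9:05, 9:10, 9:35 and 10:05.

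Both days have a baseline at 8:55. The table has no alternative version for the reverse order and no note on how to adapt it.

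Item c of the same section (Design timing) sets the rule in words. On duration: "TSST takes 15 minutes, and the imagery takes 5 minutes". On the first measurement: "At the end of the stressor of drug cue, a salivary sample will be collected to assay cortisol", with physiological and subjective measures taken then as well. On the rest: "Measurements will also be obtained at 5- 30-, and 60-minutes post-task".

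In section C.2.d the Aim 1 analysis takes in every one of these measurements: "multilevel longitudinal GLMMs will be developed using all post-stressor and post-cue data". Treatment arms are then compared at each time point.

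**The concern.** The text ties sampling to the end of the task. The table ties it to the day. The two tasks differ in length by 10 minutes, so one list of clock times per day cannot suit both tasks, although each day's slot is labelled for both.

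The measurements concerned are craving, subjective stress, heart rate, blood pressure and cortisol after each task. Craving and stress response in the laboratory are the Aim 1 outcomes, and Aim 1 is one of the two aims on which the trial is powered. If some sessions follow the table and others the text, one nominal time point would pool samples taken 10 minutes apart. For the TSST it could also pool samples taken during the task with samples taken after it.

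**Working it through.** **Inputs.** From Table 3: task start 9:00 on both days, and the two lists of measurement times. From item c: TSST 15 minutes, imagery 5 minutes, intended offsets 0, 5, 30 and 60 minutes after task end.

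**Formula.** Offset = Table 3 time - (9:00 + task duration). The TSST therefore ends at 9:15 and the imagery at 9:05.

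**TSST first: the plan's own figures are reproduced.**

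- Day 1 TSST (ends 9:15): 9:15, 9:20, 9:45, 10:15 give 0, +5, +30, +60.
- Day 2 imagery (ends 9:05): 9:05, 9:10, 9:35, 10:05 give 0, +5, +30, +60.

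**Imagery first: they are not.**

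| Day and task | Ends | Offsets from Table 3 (min) | Intended (min) | Difference (min) |
|---|---|---|---|---|
| Day 1 imagery | 9:05 | +10, +15, +40, +70 | 0, 5, 30, 60 | +10 at all four |
| Day 2 TSST | 9:15 | -10, -5, +20, +50 | 0, 5, 30, 60 | -10 at all four |

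Two of the four TSST samples, at 9:05 and 9:10, precede the end of the task. Item d divides the TSST into 5 minutes of preparation, 5 of speech and 5 of arithmetic, so these fall at the end of preparation and the end of the speech. The other two do come after the task, but 10 minutes early.

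**Baseline.** 9:00 - 8:55 = 5 minutes before either task in either order, as item c intends.

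**How many samples could be affected.** Let p be the share of participants who do the imagery first, and q the share of their TSST sessions that are run from the table. The share of all nominally post-TSST samples taken during the task is p x q x 2/4. The documents give neither p nor q. Assuming p = 0.5, the share is 0 if q = 0 and 0.5 x 1 x 2/4 = 25% if q = 1.

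**Whether the model absorbs the shift.** In the imagery-first order the displacement is +10 minutes for one task and -10 for the other, an average of (10 - 10)/2 = 0. One order coefficient shared by both tasks cannot represent two opposite displacements. If each task had its own model, an order term could take up a constant difference in level, but not one that varies with how fast the response is changing at each time point.

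**The case against.** There is a good case that this is only an incomplete table. Item c already states the right rule, tied to the task, and the corrected times follow from it and a 9:00 start. The table's times fit the first-named task on each day exactly, so it can be read as an example of the TSST-first order. The text cites Table 2 but never Table 3, and nothing gives the table priority. The TSST as described runs without a break, so stopping for saliva, a cuff reading and several rating scales at 9:05 and 9:10 would disrupt it visibly, and staff would probably notice. Finally, section C.2.d promises to examine relevant interactions, which does not exclude terms combining order with task or time.

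Most of this stands, and it limits the point to sessions actually run from the table. It does not remove the point. Table 3 is the only clock schedule in the protocol, it is labelled for both orders, and nothing marks it as an example. Its Day 1 window of 15 minutes, offered for either task, itself conflicts with a 5-minute imagery task. The imagery error would also be easy to miss: staff need only wait until 9:15 after a script that ended at 9:05. The interactions to be examined are not named, so they cannot be relied on to correct the timing.

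**Conclusion.** Table 3 contradicts item c for one of the two task orders. Where the table is followed in that order, all eight post-task measurements are displaced by 10 minutes, late for imagery and early for the TSST, and two of them fall inside the TSST. The arithmetic rests only on the printed times and durations. The likely consequence is added noise or dilution in the Aim 1 time-point comparisons, including the treatment-by-sex comparison.

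A reader might infer more than the documents support:

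- *That half the participants are mistimed, or that a quarter of post-TSST samples are taken during the task.* Both figures need equal numbers in each order and literal use of the table in every imagery-first session. The documents state no order ratio, and the continuous TSST procedure makes literal use on that day unlikely.
- *That the lofexidine-placebo contrast is biased.* This would require order to differ between arms. The documents do not say that order is balanced within arm or sex, but nothing in them suggests that it is not.
- *That the peak response to imagery is missed.* The documents give no time course for that response. They show only that the task-end and 5-minute samples would be replaced by samples at 10 and 15 minutes.

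The correction is worth making because the schedule feeds a powered aim and the remedy is nearly free.

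**What to change.** Relabel Table 3 by task, to apply on whichever day the task falls:

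- TSST session: task 9:00-9:15; measurements at 9:15, 9:20, 9:45 and 10:15.
- Imagery session: task 9:00-9:05; measurements at 9:05, 9:10, 9:35 and 10:05.

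Stating the times as minutes from task end would serve equally well. Either form gives 0, 5, 30 and 60 minutes in both orders.

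Record the actual time of task end and of each sample, and have section C.2.d define the time variable as minutes from task end.

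For sessions already completed, check the recorded times first. Treat a sample as not post-task only where the record shows that it was taken during the task; there is no ground for excluding samples on the strength of the table alone.

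The cost is a corrected table, one recorded or derived time variable and a check of existing session records. No visit or sample is added.
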